### Specific Immune-mediated Reactions

Adverse Events	Severity Grade of the Event (NCI CTCAE version 4.03)	Dose Modifications	Toxicity Management
		
For Grade 4:  Permanently discontinue study drug/study regimen.
	
 
- If no improvement within 3 to 5 days despite IV corticosteroids, consider additional workup and promptly treat with additional immunosuppressants (eg, IV IG).
 
- Once stable, gradually taper steroids over <math>\geq 28</math> days.
 

Peripheral neuromotor syndromes   (such as Guillain-Barre and myasthenia gravis)
	Any Grade	General Guidance	
For Any Grade:
 
 
- The prompt diagnosis of immune-mediated peripheral neuromotor syndromes is important, since certain patients may unpredictably experience acute decompensations that can result in substantial morbidity or in the worst case, death. Special care should be taken for certain sentinel symptoms that may predict a more severe outcome, such as prominent dysphagia, rapidly progressive weakness, and signs of respiratory insufficiency or autonomic instability.
 
- Patients should be evaluated to rule out any alternative etiology (eg, disease progression, infections, metabolic syndromes or medications). It should be noted that the diagnosis of immune-mediated peripheral neuromotor syndromes can be particularly challenging in patients with underlying cancer, due to the multiple potential confounding effects of cancer (and its treatments) throughout the neuraxis. Given the importance of prompt and accurate diagnosis, it is essential to have a low threshold to obtain a neurological consult.
 
- Neurophysiologic diagnostic testing (eg, electromyogram and nerve conduction investigations, and “repetitive stimulation” if myasthenia is suspected) are routinely indicated upon suspicion of such conditions and may be best facilitated by means of a neurology consultation.
 
- It is important to consider that the use of steroids as the primary treatment of Guillain-Barre is not typically considered effective. Patients requiring treatment should be
 

### Specific Immune-mediated Reactions

Adverse Events	Severity Grade of the Event (NCI CTCAE version 4.03)	Dose Modifications	Toxicity Management
			started with IV IG and followed by plasmapheresis if not responsive to IV IG.
	Grade 1	No dose modifications.	
For Grade 1:
 
 
– Discuss with the study physician.
 
– Care should be taken to monitor patients for sentinel symptoms of a potential decompensation as described above.
 
– Obtain a neurology consult unless the symptoms are very minor and stable.
 

	Grade 2	Hold study drug/study regimen dose until resolution to Grade $\leq 1$ .  Permanently discontinue study drug/study regimen if it does not resolve to Grade $\leq 1$ within 30 days or if there are signs of respiratory insufficiency or autonomic instability.	
For Grade 2:
 
 
– Discuss with the study physician.
 
– Care should be taken to monitor patients for sentinel symptoms of a potential decompensation as described above.
 
– Obtain a neurology consult
 
– Sensory neuropathy/neuropathic pain may be managed by appropriate medications (eg, gabapentin or duloxetine).
 
 
MYASTHENIA GRAVIS:
 
 
○ Steroids may be successfully used to treat myasthenia gravis. It is important to consider that steroid therapy (especially with high doses) may result in transient worsening of myasthenia and should typically be administered in a monitored setting under supervision of a consulting neurologist.
 
○ Patients unable to tolerate steroids may be candidates for treatment with plasmapheresis or IV IG. Such decisions are best made in consultation with a neurologist, taking into account the unique needs of each patient.
 

### Specific Immune-mediated Reactions

Adverse Events	Severity Grade of the Event (NCI CTCAE version 4.03)	Dose Modifications	Toxicity Management
			
 
○ If myasthenia gravis-like neurotoxicity is present, consider starting AChE inhibitor therapy in addition to steroids. Such therapy, if successful, can also serve to reinforce the diagnosis.
 
 
GULLAIN-BARRE:
 
 
○ It is important to consider here that the use of steroids as the primary treatment of Guillain-Barre is not typically considered effective.
 
○ Patients requiring treatment should be started with IV IG and followed by plasmapheresis if not responsive to IV IG.
 

	Grade 3 or 4	
For Grade 3:
 
Hold study drug/study regimen dose until resolution to Grade <math>\leq 1</math>.
 
Permanently discontinue study drug/study regimen if Grade 3 irAE does not resolve to Grade <math>\leq 1</math> within 30 days or if there are signs of respiratory insufficiency or autonomic instability.
 
For Grade 4:
 
Permanently discontinue study drug/study regimen.
	
For Grade 3 or 4 (severe or life-threatening events):
 
 
– Discuss with study physician.
 
– Recommend hospitalization.
 
– Monitor symptoms and obtain neurological consult.
 
 
MYASTHENIA GRAVIS:
 
 
○ Steroids may be successfully used to treat myasthenia gravis. They should typically be administered in a monitored setting under supervision of a consulting neurologist.
 
○ Patients unable to tolerate steroids may be candidates for treatment with plasmapheresis or IV IG.
 
○ If myasthenia gravis-like neurotoxicity present, consider starting AChE inhibitor therapy in addition to steroids. Such therapy, if successful, can also serve to reinforce the diagnosis.
 

### Specific Immune-mediated Reactions

Adverse Events	Severity Grade of the Event (NCI CTCAE version 4.03)	Dose Modifications	Toxicity Management
			
GUILLAIN-BARRE:
 
 
○ It is important to consider here that the use of steroids as the primary treatment of Guillain-Barre is not typically considered effective.
 
○ Patients requiring treatment should be started with IV IG and followed by plasmapheresis if not responsive to IV IG.
 

a ASCO Educational Book 2015 “Managing Immune Checkpoint Blocking Antibody Side Effects” by Michael Postow MD.  
b FDA Liver Guidance Document 2009 Guidance for Industry: Drug Induced Liver Injury – Premarketing Clinical Evaluation.

ACHe Acetylcholine esterase; ADL Activities of daily living; AE Adverse event; ALP Alkaline phosphatase test; ALT Alanine aminotransferase; AST Aspartate aminotransferase; BUN Blood urea nitrogen; CT Computed tomography; CTCAE Common Terminology Criteria for Adverse Events; ILD Interstitial lung disease; irAE Immune-related adverse event; IG Immunoglobulin; IV Intravenous; GI Gastrointestinal; LFT Liver function tests; LLN Lower limit of normal; MRI Magnetic resonance imaging; NCI National Cancer Institute; NCCN National Comprehensive Cancer Network; PCP ; PO By mouth; T3 Triiodothyronine; T4 Thyroxine; TB Total bilirubin; TNF Tumor necrosis factor; TSH Thyroid-stimulating hormone; ULN Upper limit of normal.

**Table 2. Infusion-related Reactions Associated with Durvalumab**

Severity Grade of the Event (NCI CTCAE version 4.03)	Dose Modifications	Toxicity Management
Any Grade	General Guidance	For Any Grade: 
 
– Manage per institutional standard at the discretion of investigator.
 
– Monitor patients for signs and symptoms of infusion-related reactions (eg, fever and/or shaking chills, flushing and/or itching, alterations in heart rate and blood pressure, dyspnea or chest discomfort, or skin rashes) and anaphylaxis (eg, generalized urticaria, angioedema, wheezing, hypotension, or tachycardia).
 

Grade 1 or 2	
For Grade 1:
 
The infusion rate of study drug/study regimen may be decreased by 50% or temporarily interrupted until resolution of the event.
 
For Grade 2:
 
The infusion rate of study drug/study regimen may be decreased 50% or temporarily interrupted until resolution of the event.
 
Subsequent infusions may be given at 50% of the initial infusion rate.
	For Grade 1 or 2: 
 
– Acetaminophen and/or antihistamines may be administered per institutional standard at the discretion of the investigator.
 
– Consider premedication per institutional standard prior to subsequent doses.
 
– Steroids should not be used for routine premedication of Grade <math>\leq 2</math> infusion reactions.
 

Grade 3 or 4	
For Grade 3 or 4:
 
Permanently discontinue study drug/study regimen.
	For Grade 3 or 4: 
 
– Manage severe infusion-related reactions per institutional standards (eg, IM epinephrine, followed by IV diphenhydramine and ranitidine, and IV glucocorticoid).
 

CTCAE Common Terminology Criteria for Adverse Events; IM Intramuscular; IV Intravenous; NCI National Cancer Institute.

**Table 3. Non-immune-mediated Reactions Associated with Durvalumab**

Severity Grade of the Event (NCI CTCAE version 4.03)	Dose Modifications	Toxicity Management
Any Grade	Note: Dose modifications are not required for AEs not deemed to be related to study treatment (ie, events due to underlying disease) or for laboratory abnormalities not deemed to be clinically significant.	Treat accordingly, as per institutional standard.
Grade 1	No dose modifications.	Treat accordingly, as per institutional standard.
Grade 2	Hold study drug/study regimen until resolution to ≤Grade 1 or baseline.	Treat accordingly, as per institutional standard.
Grade 3	Hold study drug/study regimen until resolution to ≤Grade 1 or baseline.  For AEs that downgrade to ≤Grade 2 within 7 days or resolve to ≤Grade 1 or baseline within 14 days, resume study drug/study regimen administration. Otherwise, discontinue study drug/study regimen.	Treat accordingly, as per institutional standard.
Grade 4	Discontinue study drug/study regimen (Note: For Grade 4 labs, decision to discontinue should be based on accompanying clinical signs/symptoms, the Investigator’s clinical judgment, and consultation with the Sponsor.).	Treat accordingly, as per institutional standard.

Note: As applicable, for early phase studies, the following sentence may be added: “Any event greater than or equal to Grade 2, please discuss with Study Physician.”

AE Adverse event; CTCAE Common Terminology Criteria for Adverse Events; NCI National Cancer Institute.

Abbreviations:

AChE = acetylcholine esterase; ADA = American Dietetic Association; AE = adverse event; ALP = alkaline phosphatase; ALT = alanine aminotransferase; AST = aspartate aminotransferase; CT = computed tomography; GI = gastrointestinal; IDS=Infectious Disease Service; ILD = interstitial lung disease; IM = intramuscular; irAE = immune-related adverse event; IV = intravenous; NCI CTCAE = National Cancer Institute Common Terminology Criteria for Adverse Events; PO = by mouth; TNF = tumor necrosis factor; TSH = thyroid stimulating hormone; ULN = upper limit of normal.

### **6.5.2 Radiation therapy toxicity evaluation and management**

Acute radiation toxicities are those that occur within 90 days from therapy start and will be graded according to CTCAE v4.03. Toxicities related to RT differ based on the location of the treated lesion(s) and are related to dose received by OARs near the targeted lesion. The majority of lesions that receive ER on this study are anticipated to be in the thorax and abdomen based on the patterns of spread of pancreatic cancer. The most common sites of distant metastases are the liver, abdominal peritoneum, and lungs. Accordingly, the most likely potential acute radiation adverse events include fatigue, dermatitis, pneumonitis, esophagitis, colitis, hepatitis, nausea, vomiting, anorexia, and diarrhea.

RT should be continued without interruption, if possible. Grade 3 or higher acute toxicity from RT is not expected and is not expected to lead to RT interruption. However, Grade 3 or higher acute toxicity may necessitate a treatment break. If a treatment delay for acute toxicity is required, the total radiation dose and dose per fraction will not be modified. Any missed radiation fractions should be made up as quickly as possible; if needing to give RT and durvalumab on the same day then the RT should be given first, if possible. It should be noted that any Grade 3-5 acute radiation toxicity counts toward the early stopping rule.

Patients will be evaluated by a radiation oncologist at least once weekly during RT (Weeks 2 and 4) for physical examination and toxicity evaluation. Patients will be seen at least every 4 weeks by a radiation oncologist or medical oncologist thereafter starting in Week 8.

Late toxicities are those that occur after 90 days of therapy start and will be graded according to CTCAE v4.03. Late toxicities, like acute toxicities, are related to dose received by OARs near the targeted lesion.

### **6.5.3 Toxicity management guidelines for combination treatment regimen**

Acute toxicity attributable to RT and not durvalumab should be managed accordingly with optimal supportive care measures. If toxicity clearly related to RT and not durvalumab  $\geq$  Grade 3 is persistent, then a RT break is allowable until the toxicity decreased to  $<$  Grade 3. Durvalumab should be continued during the RT break provided that there are no documented toxicities from durvalumab that would necessitate holding durvalumab. If durvalumab is held due to toxicity attributed solely to the durvalumab, then the RT should also be held until durvalumab is resumed. Once durvalumab is resumed, RT should also be resumed.

In addition to the individual toxicity management guidelines for durvalumab and RT described above, Table 4 outlines what actions are recommended for the management of any potential overlapping toxicities that may occur following treatment with this combination (e.g., which agent should be modified first, etc.).

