### **5.2.2 Technical Factors**

Only photon therapy is permitted and energies  $\geq 6\text{MV}$  are required. Cobalt-60, electron, and charged particle therapies are not permitted. Treatment for each lesion should begin on a Monday and finish on a Wednesday when possible. RT is scheduled to be delivered daily on Days 15-17 and Days 29-31.

Because multiple lesions will sequentially receive RT, multiple isocenters should be used with each centered on a separate lesion.

Composite plans should be generated to account for normal tissue dose from each lesion that is treated. Dose summation from multiple treatment sites should be determined on a single CT scan that encompasses the relevant anatomic region. A planning CT dataset that includes all targets and relevant critical structures in the imaging study should be obtained when possible. When this is not possible due to the size of the imaging study, CT datasets should be divided into two parts and treatment fields should be adjusted

so that dose spillage from the treatment of targets in one dataset to the next is minimal such that the dose contributions do not require summation.

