### 5.2.5 Missed treatments

Missed treatments and treatment breaks should be entered into the treatment record. Any missed treatments should be made up so that the total prescribed radiation dose is delivered. This should be done as expeditiously as possible and must respect time needed off treatment for any patients who experience significant toxicity. Management of acute treatment-related toxicity is described in Table 1. More than one fraction should not be delivered per day to make up treatments although treatment on Saturday/Sunday is permitted.

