### **6.3 Dosage and Administration**

All subjects will receive durvalumab 1500 mg IV (or 20mg/kg IV if <30 kg) Q4W starting on Day 1. This will continue until a maximum of 13 administrations (48 weeks) of durvalumab is given, progressive disease, or unacceptable toxicity, whichever occurs first. The dose of durvalumab will not change during this study. Refer to Section 5.1.4 and 5.1.5 for details regarding administration and monitoring of administration of durvalumab. If the scheduled day of durvalumab administration is missed (e.g. patient illness, holiday, etc) then durvalumab administration should be given the next day possible, or at least within 3 days, and any delays in durvalumab administration should be as limited as possible.

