### Specific Immune-mediated Reactions

Adverse Events	Severity Grade of the Event (NCI CTCAE version 4.03)	Dose Modifications	Toxicity Management
			
(eg, infliximab at 5 mg/kg every 2 weeks). Caution: It is important to rule out sepsis and refer to infliximab label for general guidance before using infliximab.
 
 
- Once the patient is improving, gradually taper steroids over <math>\geq 28</math> days and consider prophylactic antibiotics, antifungals, or anti-PCP treatment (refer to current NCCN guidelines for treatment of cancer-related infections (Category 2B recommendation)a
 
- Consider pulmonary and infectious disease consult.
 
- Consider, as necessary, discussing with study physician.
 

	
Grade 3 or 4  (Grade 3: severe symptoms; limiting self-care ADL; oxygen indicated)
 
(Grade 4: life-threatening respiratory compromise; urgent intervention indicated [eg, tracheostomy or intubation])
	
Permanently discontinue study drug/study regimen.
	
For Grade 3 or 4 (severe or new symptoms, new/worsening hypoxia, life-threatening):
 
 
- Promptly initiate empiric IV methylprednisolone 1 to 4 mg/kg/day or equivalent.
 
- Obtain pulmonary and infectious disease consult.
 
- Hospitalize the patient.
 
- Supportive care (eg, oxygen).
 
- If no improvement within 3 to 5 days, additional workup should be considered and prompt treatment with additional immunosuppressive therapy such as TNF inhibitors (eg, infliximab at 5 mg/kg every 2 weeks dose) started. Caution: rule out sepsis and refer to infliximab label for general guidance before using infliximab.
 
- Once the patients is improving, gradually taper steroids over <math>\geq 28</math> days and consider prophylactic antibiotics, antifungals, and, in particular, anti-PCP treatment (refer to current NCCN guidelines for treatment of cancer-related infections (Category 2B recommendation).a
 

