## 11.2 Statistical analysis plan

### 11.2.1 Continuous toxicity monitoring in the first 20 patients enrolled (stopping rule)

Continuous toxicity monitoring will occur for the first 20 patients enrolled. The endpoint is severe (G3-5) acute non-hematologic toxicity. G3-5 non-hematologic occurs in <10% of patients treated with the anti-PD-1/PD-L1 mAb alone (Robert, Ribas et al. 2014). Early stopping for unexpected, severe early toxicity is based on continuous monitoring of G3-5 toxicity with the aim of keeping the probability of early stopping at around 5% if the true underlying rate of this toxicity is 10%. Following Ivanova et al. (Ivanova, Qaqish et al. 2005), we use the boundary proposed by Pocock (Pocock 1977). Values of  $b_k$  for the current design are given in Table 1.

Table 1. Pocock boundary for early stopping due to grade 3+ toxicity with a probability of stopping of about  $\phi = 0.05$  and assuming the true toxicity rate is  $\theta_0 = 0.1$

k	1	2	3	4	5	6	7	8	9	10	11	12	13	14	15	16	17	18	19	20
<math>b_k</math>	–	2	3	3	3	3	4	4	4	4	4	4	5	5	5	5	5	6	6	6

It is important for the validity and practical implementation of this strategy that the sequence of patients entered into the study is strictly recorded and preserved. Ideally, the design assumes that the outcome, i.e. the incidence of G3+ toxicity among the first  $i$  patients is known when entering patient  $i+1$ . The accrual rate is expected to be around 1-2 patients per month and the time window for observing early toxicity in a patient is pragmatically defined as the time during and within two weeks after the completion of RT; therefore, insisting on complete observations before entering the next patient will slow down accrual considerably. Instead we will allow staggered entry of cases. For patient safety reasons, no more than 6 patients will be allowed to be on active treatment at any point during the continuous toxicity monitoring portion of the trial.

If the boundary is crossed, the treatment with durvalumab and RT will be discontinued in all patients on treatment at that point in time.

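### The stopping-rule toxicity window is tied to RT: it does not clearly cover the days before RT, and it has no end if RT is not completed, a case that Section 6.5.3 makes possible

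*Combined protocol and SAP*

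**What the plan says.** **The monitoring window.** Section 11.2.1 monitors Grade 3-5 acute non-hematologic toxicity continuously in the first 20 patients enrolled. The time for observing a patient is "pragmatically defined as the time during and within two weeks after the completion of RT". Section 3.3 and the synopsis carry the same definition. Monitoring ends when 20 patients are enrolled and have completed therapy without a crossing.

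**The DLT period.** Section 6.4 places DLT evaluation in the same monitoring component. It starts at the first durvalumab dose and ends four weeks after the last radiation dose. Patients who leave earlier for a reason other than a DLT are replaced.

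**The schedule.** Durvalumab is given "Q4W starting on Day 1" (Section 6.3). For radiation, "RT is scheduled to be delivered daily on Days 15-17 and Days 29-31" (Section 5.2.2).

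**The RT hold.** Section 6.5.3 states: "If durvalumab is held due to toxicity attributed solely to the durvalumab, then the RT should also be held until durvalumab is resumed". It continues: "Once durvalumab is resumed, RT should also be resumed". Section 5.2.5 states: "Any missed treatments should be made up so that the total prescribed radiation dose is delivered", and adds that make-up must allow for time off because of significant toxicity.

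**The permanent stop.** For several severe immune events, such as Grade 3-4 pneumonitis or enterocolitis, the action in Section 6.5.1 is "Permanently discontinue study drug/study regimen". Table 2 gives the same action for Grade 3-4 infusion reactions.

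**The concern.** The boundary is the trial's only formal stopping rule. Its operating characteristics assume that each of the first 20 patients ends up classified as having had the event or not. A window defined only by RT causes two difficulties. An event between the first infusion and the start of RT is not clearly inside it. A patient who never completes RT has no date on which to be declared event-free.

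The RT-hold rule makes both cases possible, in the patients with early durvalumab toxicity. If sites read the window literally, some early durvalumab events might not count, and the error would run towards missing toxicity. The same rule can also disturb the two-week interval between RT courses, which Section 1.3 presents as priming followed by boosting.

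**Working it through.** **1. The time definitions side by side**

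| Section | Opens | Closes | On the planned schedule |
|---|---|---|---|
| 11.2.1, 3.3, synopsis | during RT (read literally) | 2 weeks after RT completion | Day 15 to 31 + 14 = Day 45 |
| 6.4 (DLT) | first durvalumab | 4 weeks after last RT dose | Day 1 to 31 + 28 = Day 59 |
| 6.5.2 (acute RT toxicity) | therapy start | 90 days | bounded without reference to RT completion |

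Section 6.5.2 adds that any Grade 3-5 acute radiation toxicity counts toward early stopping, so a third time limit bears on the same rule. The first two definitions differ at both ends. If RT is started but not completed, the 11.2.1 window has no closing date, while the 6.4 window can still be dated from the last fraction given. If RT never starts, neither can be dated. One example is a Grade 3 infusion reaction on Day 1. Table 2 requires a permanent stop, Section 6.4 can exclude the event as a DLT (first occurrence, resolved within 6 hours), and it falls before RT.

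**2. A durvalumab-only hold in force on Day 15**

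Every four weeks from Day 1 gives infusions on Days 1, 29 and 57. The documents do not define *resumed*.

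- *Next infusion given:* lesion-1 RT cannot start before Day 29, so it falls on Days 29-31, the lesion-2 days. At one fraction a day, lesion 2 is then on Days 32-34 at the earliest, or on Days 43-45 if the 14-day spacing is kept. The two-week window closes on Day 34 + 14 = 48, or 45 + 14 = 59.
- *Hold criteria cleared, no steroids:* an event that clears before Day 15 moves no RT day. The delay is 0 days.
- *Steroids used:* several rows of the immune-event table allow resumption only after the taper is complete, and the specific rows set a taper of at least 28 days. A taper starting on Day 2, 8 or 14 ends no earlier than 2 + 28 = Day 30, 8 + 28 = Day 36 or 14 + 28 = Day 42. All are past Day 29, on either reading of *resumed*.

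No section gives the order or spacing of the two courses after a hold.

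**3. A permanent durvalumab stop**

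Section 6.5.3 covers holds only. Two groups of passages point in different directions:

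- *RT ends:* the discontinuation tables refer to the regimen as well as the drug, the synopsis lists RT under investigational products, and Section 4.3 ends further investigational product.
- *RT continues:* Section 5.2.5 asks for the full RT dose to be delivered, and the product list in Section 15.1 names durvalumab alone.

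**4. Size of the effect on the boundary**

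Inputs: b_k from Table 1 of Section 11.2.1, and a true event rate p. Let f_k(x) be the probability of x events after k patients with no crossing so far. Then f_k(x) = f_{k-1}(x)(1-p) + f_{k-1}(x-1)p. Any mass at x >= b_k is moved to *stopped*, and the stopped mass is summed over k = 1 to 20.

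At p = 10% this gives 4.88%, against the stated 4.9%, so the plan's figure is reproduced. At 50% it gives 98.8%, marginally under the stated figure of more than 99%; that is unrelated to this point.

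Now take a true rate of 30% and let u percentage points of patients have events that go uncounted. The counted rate is 30 - u. The documents do not give u, so a range is shown.

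| u (points) | Counted rate | P(stop) |
|---|---|---|
| 0 | 30% | 70.0% |
| 1.5 | 28.5% | 65.1% |
| 2.6 | 27.4% | 61.2% |
| 3 | 27% | 59.8% |
| 6 | 24% | 48.4% |
| 10 | 20% | 32.8% |

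The 2.6 row uses the treatment-related discontinuation rate with durvalumab monotherapy in Section 1.2.2 (18/694). It is the nearest documented guide, because before Day 15 a patient has received durvalumab alone.

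**The case against.** The strongest reply is that the sentence in Section 11.2.1 explains why staggered entry is allowed and does not decide which events count. The endpoint is severe acute toxicity in the first 20 enrolled, monitored continuously. Section 6.4 starts at first durvalumab and names severe pneumonitis and colitis. On that view a severe event counts when it happens, and a missing end date matters mainly for declaring a patient event-free, or for stops on Grade 2 or DLT-excluded events. This is a fair reading and may be the intended one. But Section 11.2.1 offers no other definition of the observation period, and Section 6.4 closes at a different time.

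A reader might also infer stronger claims that the documents do not support:

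- *Section 6.5.3 contradicts Section 5.2.5.* Not for temporary holds, because Section 5.2.5 allows time off for toxicity. The tension is confined to permanent stops.
- *Any toxicity before Day 15 delays RT by at least 14 days.* Only toxicity that triggers a hold and is attributed solely to durvalumab is covered, and the delay can be 0 days.
- *A permanent stop leaves RT held for good.* The case is unaddressed, and the regimen wording could be read as ending RT.
- *Sections 6.5.2 and 6.5.3 conflict on same-day order.* Section 6.5.2 says "if needing to give RT and durvalumab on the same day then the RT should be given first, if possible", which is a preference, and Section 6.5.3 sets no same-day order.
- *The chance of stopping falls from 70% to 33%.* The arithmetic is right, but it needs 10% of all patients to have uncounted severe events, and nothing in the documents supports that share.

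**Conclusion.** The point holds as a defect in how the stopping rule is defined. The window in Section 11.2.1, Section 3.3 and the synopsis does not clearly include Days 1-14, has no closing date when RT is not completed, and disagrees with Section 6.4. Section 6.5.3 is a credible source of such patients, because *resumed* is undefined and RT after a permanent durvalumab stop is not settled.

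No stated number is wrong because of this. The loss of protection cannot be fixed from the documents. At a true rate of 30% the stopping probability goes from 70% to about 61% with 2.6 points uncounted. That row assumes that all such discontinuations would be severe, would arise before RT and would go uncounted. The monotherapy rate covers the whole reported treatment experience in other solid tumours, so it is a rough guide only. If sites already count from first durvalumab, no events before RT are lost, and the missing closing date remains. The change is worth making because it is cheap and concerns a safety rule.

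**What to change.** - In Section 11.2.1, Section 3.3 and the synopsis, open the counted window at the first durvalumab dose. Give it a fixed closing study day for any patient who does not complete RT, so that each of the first 20 can be classified.
- Align that window with Section 6.4 (two or four weeks after RT, and how replaced patients enter the count), and state how the 90-day limit in Section 6.5.2 relates to it.
- The sponsor should reconcile Sections 5.2.5, 6.5.2 and 6.5.3 on what *resumed* means, and on what happens to each RT course after a hold and after a permanent stop. The table that follows Section 6.5.3 belongs in the same exercise: it is cited as Table 4 but headed Table 1, and it ties the RT hold to RT toxicity having resolved below Grade 3, whereas the text ends the RT break at that point. No clinical rule is proposed here.

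The cost is a wording amendment with no extra visits. A few more events may count toward the boundary, and adopting the longer window would delay classification from Day 45 to Day 59 on the planned schedule.
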